## **Secondary Outcome Measures**

Subsequent rehospitalization will be measured using an all-cause readmission rate existing in UPMC ISD inpatient claims for physical and behavioral health service use within 30 days and again at 12 months, following the index inpatient admission. Inpatient and ED visits that were adjudicated and reclassified as Observation visits will be separately explored at 12 months.

Functional status will be measured using the PROMIS Physical Functional Form – Short For 6b which is a brief self-report tool that assesses functional impairment in everyday tasks, household chores, and walking using a 5 point Likert scale.

Quality of life will be measured using the Quality of Life Enjoyment and Satisfaction Questionnaire (Q-LES-Q-18), which is an 18-item, self-administered questionnaire monitoring enjoyment in several domains (physical health, subjective feelings, leisure time activities, social relationships).

Care satisfaction will be measured using the Patient Assessment of Chronic Illness Care (PACIC), a 20-item survey designed to provide an assessment of important aspects of care for chronic illness patients, including specific actions or qualities of care that patients report experiencing in the service delivery system and their satisfaction level.

Emergent care use will be measured using existing behavioral and physical health claims data from the UPMC ISD data warehouse determining participant frequency of emergent service use over 12 months.

Engagement in primary, specialty, mental health care will be measured using existing behavioral and physical health claims data from the UPMC ISD data warehouse determining participant frequency of non-acute visits for participants over 12 months.

Gaps in care will be assessed using Healthcare Effectiveness Data and Information Set (HEDIS) quality metrics that will be compiled using existing behavioral and physical health claims data from the UPMC ISD data warehouse. Gaps in care will be assessed for six of the most common chronic diseases present among our target population, including: asthma, chronic obstructive pulmonary disease, congestive heart failure, coronary artery disease, diabetes, and depression.

## Covariates

Engagement in interventions will be assessed using the automatically generated usage statistics and administrative/ utilization data routinely collected for non-research purposes as part of insurance claims processing and existing payer-provider service delivery.

Patient characteristics will be obtained through self-report data and existing secondary administrative data on age, gender, race/ethnicity, and insurance type.

Technology/digital literacy will be measured using a series of questions from the Health Information National Trends Survey (HINTS) to assess comfort and experience with use of different. communication channels, including the Internet, to obtain vital health information for themselves and their loved ones.

Social support will be measured using the Interpersonal Support Evaluation List (ISEL), a 12-item measure designed to assess the perceived availability of three types of social support (appraisal, belonging, and tangible).

Health literacy will be measured using the first ten items of the All Aspects of Health Literacy Scale (AAHLS), a 13-item survey designed to assess functional, communicative, and critical health literacy. The final three items on the AAHLS are part of an 'empowerment scale' that is not related to the outcomes of this study.

Illness complexity will be measured using the age-adjusted Charlson Comorbidity Index (CCI) which was developed as a prognostic burden of comorbid disease and is currently used by the UPMC ISD. A score will be computed at baseline based on the previous 12 months of claims, adding assigned weights for specific diseases as classified by using International Classification of Diseases (ICD) diagnoses on claims records, and age adjusting by adding 1 point for every decade over 40 to the CCI score.

Socioeconomic status will be measured using the Area Deprivation Index (ADI), which uses 17 different socioeconomic indicators to determine a deprivation score for a given neighborhood. Scores are reported in the form of quintiles, with a higher quintile indicating a higher degree of deprivation.

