For the tests of interactions, we have identified, a priori, eight subgroups of interest: those aged 60 years and above, constituting 23% of the sample, and those aged below 60; race with non-white participants constituting 38% of the sample (n=203 High-Touch/High-Tech, n=100 ODP), and white participants; Charlson Comorbidity Index Score of five or above, indicating higher illness complexity includes 54% of the sample versus lower illness complexity; and positive (opposed to negative) for comorbid behavioral health conditions for 60% of the sample. We are only presenting power analysis results for the treatment by age interactions since we do not have any a-priori hypotheses about the direction of differential effects for treatment by race, treatment by illness complexity, or treatment by comorbid behavioral health condition. All such interactions will therefore be labeled as purely exploratory in subsequent findings and publications. Power estimates for interactions were calculated based on a 2-way factorial design and the average sample size across groups. For readmission rates, we used a normal approximation to estimate the standard deviation and applied a 2-way ANOVA as similar procedures are not available for dichotomous outcomes without approximating as normal.

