Our models will be based on an intent-to-treat principle as we do not expect large drop out or non-adherence. We will employ linear regression models for continuous outcomes, logistic regression for dichotomous outcomes, and Poisson regression or negative binomial models (in the case of over-inflated variance) for count outcomes. We will fit multivariate models with the key independent variable of interest being the main effect of treatment with main effects for additional covariates included to produce an adjusted estimate of the treatment effect. These covariates will be defined a priori and will be divided into two subgroups. The first set of clinically-important covariates will be included in all models including age, race, gender, insurance type, illness complexity, and socio-economic status. The second set of covariates will be defined as engagement in interventions, social support, health literacy, and technology literacy. To address Aim 2, separate models will be fit for each a priori defined heterogeneity of treatment group (HTE) subgroup of interest. As listed below, we will test the interaction of treatment with the covariate defining the HTE subgroup.

The objective of Aim 2 is to determine whether the intervention works better for some than for others. Our pre-specified analysis plan will examine differences in main outcomes for

several subgroups. These subgroups are determined by our stakeholders to be most relevant so that end results can meaningfully inform patients about what works best for whom, and in turn, better supports individuals with MCC as they navigate the health care system and make decisions about their care. Furthermore, in examining differential impact of the interventions based on these subgroups, providers, payers, and other decision makers can target resources in a manner that best meets the needs of those in services, reduces variations in practice, and improves health outcomes.

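### The exploratory illness-complexity interaction uses an age-adjusted Charlson score in a model without a treatment-by-age term, so part of any age interaction can show up as a complexity interaction

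*Combined protocol and SAP*

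**What the plan says.** Under Covariates, illness complexity is the age-adjusted Charlson index, computed at baseline from the previous 12 months of claims, with age entering by "age adjusting by adding 1 point for every decade over 40 to the CCI score". No score without age points is defined.

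Sample Size and Power Calculations lists the Aim 2 subgroups. Two of the splits are "those aged 60 years and above, constituting 23% of the sample" and "Charlson Comorbidity Index Score of five or above, indicating higher illness complexity includes 54% of the sample versus lower illness complexity". Only the age interaction has a power calculation. The illness-complexity interaction is labelled exploratory there, and Quantitative Analysis adds that exploratory subgroups are pursued only if the overall analysis is significant.

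On modelling, Quantitative Analysis says that "separate models will be fit for each a priori defined heterogeneity of treatment group (HTE) subgroup of interest" and that "we will test the interaction of treatment with the covariate defining the HTE subgroup". Other covariates enter as main effects: "The first set of clinically-important covariates will be included in all models including age, race, gender, insurance type, illness complexity, and socio-economic status". No model with both the age and the complexity interaction is specified, and neither is an age-stratified look at complexity.

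**The concern.** The two subgroup variables overlap by construction. Reading the age points as one per completed decade past 40, a person under 50 needs 5 disease points to reach the high-complexity group, a person aged 50-59 needs 4, and a person aged 60-69 needs 3. The high-complexity group will therefore tend to hold more of the older participants.

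The complexity model adjusts for age as a predictor of outcome, but it does not let the treatment effect vary with age. If it does vary, the treatment-by-complexity term is the only interaction in the model that can pick this up. The plan itself expects a large age interaction on readmission. Aim 2 is meant to show for whom each strategy works and to let payers and providers direct resources accordingly, so a difference driven by age could be credited to disease burden.

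**Working it through.** **The plan's own figure.** The only stated interaction power for readmission is 79.8%, for age. It uses rates of 22/40/42% (High-Touch/High-Tech/ODP) in older and 18/16/28% in younger participants.
- For a 2×3 ANOVA with equal cells, n = 1,120/6 ≈ 187. The interaction residuals are ∓0.05, ±0.05 and 0, so their squares sum to 4 × 0.0025 = 0.01, and λ = n × 0.01/σ².
- With σ² = 0.277 × 0.723 = 0.200, λ = 9.33 and power is 78.5%.
- With σ² equal to the mean within-cell variance, 0.190, λ = 9.83 and power is 80.7%.

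The stated figure lies between the two. The same method gives the stated 72.2% for PAM and 99.5% for SF-36. No figure is stated for the complexity interaction.

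**Size of the leak.** Inputs from the power section are 23% aged 60 or over, 54% scoring 5 or more, and the rates above. High-Touch minus High-Tech is 22 - 40 = -18 points in older and 18 - 16 = +2 in younger participants, a 20-point age interaction. Let q be the share of those aged 60 or over who score 5 or more. The documents do not give q. It is an assumption, shown from 0.54 (no association) to 1.00. Suppose that, within each age group, the treatment effect does not depend on complexity. Then:
- older share of the high group: H = 0.23q/0.54
- older share of the low group: L = 0.23(1 - q)/0.46
- apparent complexity interaction: -20 × (H - L) points

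| q | H | L | High group (points) | Low group (points) | Apparent interaction (points) |
|---|---|---|---|---|---|
| 0.54 | 0.230 | 0.230 | -2.6 | -2.6 | 0 |
| 0.70 | 0.298 | 0.150 | -4.0 | -1.0 | -3.0 |
| 0.80 | 0.341 | 0.100 | -4.8 | 0.0 | -4.8 |
| 0.90 | 0.383 | 0.050 | -5.7 | +1.0 | -6.7 |
| 1.00 | 0.426 | 0.000 | -6.5 | +2.0 | -8.5 |

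The most that can transfer is 8.5/20, about 43% of the age interaction. The same weights applied to the plan's other age scenarios give at most 8 × 0.426 = 3.4 points for PAM and 2 × 0.426 = 0.9 points for SF-36.

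**Effect on the test.** These mixtures are unadjusted risk differences, so the logistic likelihood-ratio test was also simulated: 448/448/224 participants, 1,500 trials per value of q, the plan's age-specific rates, no true complexity interaction, and main effects for age (as a 60-or-over indicator) and complexity.

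| q | Complexity test, separate model as planned | Complexity test, treatment-by-age added | Age-interaction power, own model | Age-interaction power, joint model |
|---|---|---|---|---|
| 0.54 | 5.5% | 5.3% | 68% | 68% |
| 0.70 | 8.1% | 5.3% | 72% | 70% |
| 0.80 | 10.9% | 5.2% | 70% | 65% |
| 0.90 | 17.2% | 4.9% | 69% | 60% |
| 1.00 | 25.9% | 4.4% | 71% | 53% |

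The Monte Carlo standard error near 5% is √(0.05 × 0.95/1,500) ≈ 0.6 points, so 5.5% at q = 0.54 is consistent with the nominal level.

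**Prognostic age effect only.** With age raising risk equally in all arms (log-odds 0.8, q = 0.90), the planned complexity test rejects 4.7% of the time. The age main effect deals with that case.

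**The case against.** The strongest reply is that the consequence is contained. The complexity interaction has no directional hypothesis, is labelled exploratory, and is taken further only after a significant overall result. Collinearity checks are promised and would reveal the overlap. The age-adjusted index is the payer's own score, so asking whether effects differ above and below it is a legitimate operational question, and randomised comparisons within each score group are valid. The size of the leak depends on an overlap the documents do not give. At overlaps of 70% to 90% a false positive is still the exception (8% to 17%), and for SF-36 the leak is under 1 point against a planning SD of 10.

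Most of this stands, and it is why the point is minor. Three parts do not dispose of it. The exploratory label warns of weak evidence, not of a difference credited to the wrong variable. Collinearity diagnostics do not add the missing interaction term. The condition on the overall analysis gives little protection if it means the three-arm comparison. Under the plan's age-specific rates the arm averages are 0.23 × 22 + 0.77 × 18 = 18.9%, and likewise 21.5% and 31.2%. A three-arm chi-squared test with 448/448/224 then has about 92% power (noncentrality 13.3), so the condition would usually be met in the very scenario where the leak arises.

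A reader might infer more: that any age effect will appear as a complexity effect, or that Aim 2 cannot tell the two apart. The documents support neither. Age is a main effect in every model, so a prognostic age effect is adjusted for. Age and the claims diagnoses are both collected, and the subgroups are not the same people: even at q = 1.00, (0.54 - 0.23)/0.77 = 40% of those under 60 would score 5 or more. Both interactions can be estimated; the plan does not specify the model that does it.

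**Conclusion.** The point holds as a minor gap in the exploratory part of Aim 2. As written, the complexity model can credit to illness complexity part of a treatment-by-age interaction. On the plan's readmission scenario the spurious contrast is 0 to -8.5 points and the false-positive rate is 5.5% to about 26%, depending on the overlap. The built-in age points make an overlap above 54% likely, but its value is unknown.

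These figures assume the plan's hypothesised age-specific rates, no true complexity interaction, and effect modification that changes only at age 60. If treatment effects do not differ by age, nothing leaks. The primary comparisons, the powered age interaction and the within-subgroup comparisons are not called into question. What is affected is the explanation given for a difference between complexity groups.

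**What to change.** In Quantitative Analysis, add treatment-by-age to the illness-complexity interaction model, at least as a pre-specified sensitivity analysis, and state how age is coded. Leave the powered age model as it is, because the joint model lowers power for the age interaction (for example from 69% to 60% at an overlap of 90%). Report the age-by-complexity cross-tabulation so that readers can see the actual overlap.

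Optionally, repeat the analysis with the Charlson score without age points. On its own this is incomplete: it removes the built-in overlap but not any natural correlation between age and comorbidity. It also needs a re-derived cut and prevalence in place of 5 and 54%, and it departs from the payer's score.

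No new data are needed. The cost is a sentence or two in the SAP, one table, and somewhat less precision for a complexity interaction that was never powered. In the scenario simulated, the complexity test returns to about its nominal level (4.4% to 5.3%).

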# **Study Population**

Medicaid or dual-eligible adults aged 21 years and older with MCC, including at least one physical health condition and at least one additional physical or behavioral health condition and are beneficiaries/members of our partnering health care payer. In addition, these individuals are identified as high risk for unplanned care use including rehospitalization. Our study population is representative of the majority of Medicaid and dual-eligible beneficiaries and accords with a national sample.

# Inclusion/Exclusion Criteria

## **Inclusion Criteria**

Individuals who are (1) Medicaid or dual-eligible; (2) age 21 years and older; (3) insured through physical and/or behavioral health payers within the UPMC ISD; (4) identified as members high risk for high utilization including rehospitalization and have had an inpatient hospital stay within the last 30 days; (5) who have at least one physical health condition (e.g. cardiovascular disease, hypertension, COPD, diabetes) and at least one additional physical or behavioral health condition (e.g. depression, serious mental illness, substance abuse disorder); and (6) who reside in Pennsylvania.

## **Exclusion Criteria**

Individuals who are (1) pregnant; (2) in skilled nursing facilities; (3) on hemodialysis for kidney disease; (4) in active cancer treatment; and/or (5) unable to speak, read, or understand English or Spanish at the minimum-required level.

# **Study Duration/Study Timeline**

January 1, 2018 – April 14, 2018: Pre-Implementation Period April 15, 2018 – December 31, 2022: Implementation Period January 1, 2023 – November 30, 2024: Post-Implementation Period

# **Statistical Analysis Plan**

#### Sample Size and Power Calculations

We will evaluate, based on a 20% attrition rate, a total of 1,120 participants at 12-month postenrollment data collection time point, which will be the main time point for the comparison of primary outcomes. We will use a randomization ratio of 2:2:1 (High-Touch; High-Tech; ODP, respectively) and, as such, estimate final sample sizes of n=448 for each active care strategy and n=224 for the ODP strategy. All calculations for the power estimates were done in PASS version 13. For the primary test for the trial, the power calculation is based on the comparison of the two primary care strategies (High-Touch and High-Tech) for the main outcome of hospital readmissions between the strategies, using a two-sample test of proportions; specifically we have 80% power to detect a difference between a readmission rate of 20% in the High-Touch care strategy versus 28% in the High-Tech care strategy. Additionally, for the overall differences between the three care strategies the given sample sizes yield 95% power; based on a chi-squared test.

For the additional primary outcomes of health status (SF-36) and patient activation (PAM), power estimates are based on a two-sample t-test for comparing High-Touch and High-Tech and using an Analysis of Variance (ANOVA) for an overall difference across the three arms. For SF-36 scores, we hypothesized mean increases of 11, 5 and 0 points in High-Touch, High-Tech and ODP, respectively, with a standard deviation of 10 in each arm or care strategy. This yielded over 99% power for the test between the two active interventions (e.g. High-Touch and High-Tech), assuming a 5-point increase for the High-Tech group would yield 80% power for detecting a difference as small as 1.7, which is a small effect size of 0.17. The hypothesized mean increases also yield >99% power for the overall test of mean differences across interventions and yield >90% for means as close as 5.6, 5.0 and 4.4. For PAM scores, we hypothesized mean increases of 4, 8 and 0.5 points in High-Touch, High-Tech and ODP, respectively, with a standard deviation of 20.9 in each arm. This difference, which corresponds to a small effect size of 0.19 yielded 82% power for the test between the two active intervention groups (e.g. High-Touch and High-Tech). The hypothesized mean increases also yield >99% power for the overall test of mean differences across the groups and yield >80% for means as close as 6.5, 8 and 6.

For the tests of interactions, we have identified, a priori, eight subgroups of interest: those aged 60 years and above, constituting 23% of the sample, and those aged below 60; race with non-white participants constituting 38% of the sample (n=203 High-Touch/High-Tech, n=100 ODP), and white participants; Charlson Comorbidity Index Score of five or above, indicating higher illness complexity includes 54% of the sample versus lower illness complexity; and positive (opposed to negative) for comorbid behavioral health conditions for 60% of the sample. We are only presenting power analysis results for the treatment by age interactions since we do not have any a-priori hypotheses about the direction of differential effects for treatment by race, treatment by illness complexity, or treatment by comorbid behavioral health condition. All such interactions will therefore be labeled as purely exploratory in subsequent findings and publications. Power estimates for interactions were calculated based on a 2-way factorial design and the average sample size across groups. For readmission rates, we used a normal approximation to estimate the standard deviation and applied a 2-way ANOVA as similar procedures are not available for dichotomous outcomes without approximating as normal.

For age by treatment interactions, readmission rates are hypothesized to increase in older age groups, with greater differences in the treatment effects. We also hypothesized that the intervention groups will yield similar rates in the younger group while High-Tech will be closer to ODP in the older group. More specifically, we have 79.8% power to detect a significant interaction with readmission rates of 22%, 40%, and 42% in the older group (for High-Touch, High-Tech, and ODP, respectively) and rates of 18%, 16% and 28% in the younger group. For PAM scores, we hypothesized that, in the older group, the interventions will work equally well and much more effectively than ODP, whereas, in the younger group, High-Tech will be most effective, with High-Touch and ODP showing no effect on PAM scores. More specifically, we have 72.2% power to detect a significant interaction with mean increases in PAM of 8, 8, and 1 in the older group for High-Touch, High-Tech, and ODP, respectively, and mean increases of 0, 8 and 0 in the younger group. For SF-36 scores, we assumed a greater overall effect for High-Touch and speater effect in younger ages and a slightly larger difference between ages for the

High-Touch group. Specifically, we have 99.5% power to detect a significant interaction with mean increases in SF-36 of 7, 2, and 0 in the older group for High-Touch, High-Tech, and ODP, respectively, and mean increases of 15, 8, and 1 in the younger group.

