## **Research Synopsis**

**Study Population:** Medicaid or dual-eligible (Medicare-Medicaid) adults aged 21 years and older with multiple chronic conditions (MCC), including at least one physical health condition and at least one additional physical or behavioral health condition, beneficiaries/members of our partnering health care payer, and identified as having high and/or rising health care needs and at risk for unplanned health care use.

**Study Design:** A comparative effectiveness study using an individual-level, randomized design along with a pragmatic, mixed-methods approach to compare three strategies (e.g., in-person and telephonic supported care, technology-supported care, and optimal discharge planning care) all of which include evidence-based components of integrated care. Quantitative (e.g., self-report, claims, process) and qualitative (e.g., interviews) data will be collected across multiple timepoints during the study period.

Sample Size: We expect to enroll 1,400 individuals.

Study Duration: The contract period begins January 1, 2018 and concludes November 30, 2024.

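### Three power statements for SF-36 and PAM do not follow from the plan's own inputs: over 90% computes to 25%, over 80% to 21%, and 80% for 1.7 points to 72%

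*Combined protocol and SAP*

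**What the plan says.** The Research Synopsis states: "We expect to enroll 1,400 individuals". Sample Size and Power Calculations then plans, "based on a 20% attrition rate, a total of 1,120 participants at 12-month", and from a 2:2:1 allocation the authors "estimate final sample sizes of n=448 for each active care strategy and n=224 for the ODP strategy".

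For SF-36 and PAM, the same section bases power on a two-sample t-test between High-Touch and High-Tech and on an ANOVA across the three arms. The SD is 10 for SF-36 and 20.9 for PAM. After giving power at the hypothesized mean increases, it adds three statements about smaller effects:

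- SF-36, two active arms: the sample "would yield 80% power for detecting a difference as small as 1.7" points.
- SF-36, three arms: the sample will "yield >90% for means as close as 5.6, 5.0 and 4.4".
- PAM, three arms: the sample will "yield >80% for means as close as 6.5, 8 and 6".

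It also gives more than 99% power for the three-arm PAM test at the hypothesized increases of 4, 8 and 0.5.

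**The concern.** The section disagrees with itself before any software is used. For SF-36 it gives 80% power for a gap of 1.7 points between two arms of 448. It then gives more than 90% when the widest gap among the three arms is 1.2 points (5.6 against 4.4) and one of those two arms is the small ODP arm. For PAM it gives 82% for a 4-point gap, then more than 80% when the widest gap is 2 points. The SD does not change in either case.

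SF-36 and PAM are both named as primary outcomes, and these sentences are the plan's statement of how small a difference the trial can detect on them. A reader who trusts them could take a non-significant three-arm test as evidence against differences of this size, and so read it as equivalence of the care strategies.

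**Working it through.** **Inputs.** All come from Sample Size and Power Calculations unless noted.

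- Evaluable n: 448 High-Touch, 448 High-Tech, 224 ODP (total 1,120).
- Enrolled n: 1,400 (Research Synopsis), which is 560/560/280 at 2:2:1.
- SD: 10 (SF-36), 20.9 (PAM).
- Alpha: two-sided 0.05. This is an assumption for the main tests; the Quantitative Analysis section states it only for the interaction tests.

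**Step 1. Reproduce figures that do hold.** For two arms of size n, power ≈ Φ(δ/(SD·√(2/n)) − 1.96).

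- PAM 8 vs 4: 4/(20.9 × √(2/448)) = 2.864, and Φ(0.904) = 81.7% (noncentral t 81.6%). Stated: 82%.
- Readmission 20% vs 28%, n = 448 per arm, two-sample test of proportions: 80.2%. Stated: 80%.
- SF-36 11 vs 5: above 99%, as stated.

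So 448 per active arm with two-sided 0.05 is the basis that the plan used for these figures.

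**Step 2. SF-36, 1.7 points between active arms.**

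- n = 448: 1.7/(10 × √(2/448)) = 2.544, and Φ(0.584) = 72.1% (noncentral t 72.0%). Stated: 80%.
- n = 560: 1.7/(10 × √(2/560)) = 2.845, and Φ(0.885) = 81.2% (noncentral t 81.1%).
- Difference detectable with 80% power at n = 448: (1.960 + 0.842) × 10 × √(2/448) = 1.87.
- 80% power for 1.7 needs 544 evaluable per arm.

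**Step 3. Three-arm tests.** One-way ANOVA with noncentral F on 2 and 1,117 degrees of freedom, critical value 3.004, and λ = Σ nᵢ(μᵢ − μ̄)²/SD², where μ̄ is the mean weighted by arm size. With these degrees of freedom, 80% power needs λ ≈ 9.66 and 90% needs λ ≈ 12.69.

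- SF-36 5.6/5.0/4.4: μ̄ = 0.4(5.6) + 0.4(5.0) + 0.2(4.4) = 5.12. λ = [448(0.48²) + 448(0.12²) + 224(0.72²)]/100 = 225.79/100 = 2.26. Power 25.0%.
- PAM 6.5/8/6: μ̄ = 0.4(6.5) + 0.4(8) + 0.2(6) = 7.0. λ = [448(0.5²) + 448(1²) + 224(1²)]/436.81 = 784/436.81 = 1.79. Power 20.6%.
- PAM 4/8/0.5: μ̄ = 4.9. λ = [448(0.9²) + 448(3.1²) + 224(4.4²)]/436.81 = 9,004.8/436.81 = 20.6. Power 98.7%. Stated: more than 99%.

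Simulation with 10,000 runs gave 23.9%, 20.4% and 98.7% for these three patterns.

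**Step 4. Look for a basis that would rescue the two close-means claims.** SDs are as stated.

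| Basis | SF-36 (stated >90%) | PAM (stated >80%) |
|---|---|---|
| 448/448/224 | 25.0% | 20.6% |
| Enrolled 560/560/280 | 30.4% | 24.8% |
| Equal arms, 1,120 in total | 29.1% | 21.1% |
| 448 in every arm | 34.2% | 24.6% |
| Equal arms, 1,400 in total | 35.5% | 25.5% |
| 448/448/224, alpha 0.10 | 36.3% | 31.0% |
| 448/448/224, most favourable order of means | 34.2% | 24.0% |
| 1,120 in every arm | 72.1% | 54.9% |

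At the stated SDs and allocation, the claims would need about 6,280 (SF-36) or 6,015 (PAM) evaluable participants. At the stated sizes they would need SDs of about 4.2 or 9.0.

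**Step 5. Spreads that the trial can detect.** Widening each set of means in proportion, with n and SD held as stated, reaches the claimed power at 2.37 times the SF-36 spread (6.42/5.00/3.58) and 2.32 times the PAM spread (4.52/8/3.36). Rounded to 6.4/5.0/3.6 and 4.5/8/3.4, power is 89.0% and 79.8%.

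**The case against.** Several points can fairly be made for the plan.

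- These are sensitivity statements. The section names the High-Touch versus High-Tech readmission comparison as the primary test of the trial, and that 80% reproduces. So does power at the hypothesized effects for SF-36 (both tests) and for PAM between the active arms. No design decision rests on the wrong figures. This stands, and it limits the finding to what the plan says about detectable differences.
- The 1.7-point claim is a different kind of error. It reproduces at 560 per arm, so attrition was probably left out, and a one-sided 0.05 test at 448 would also give about 81.5%. This stands in part. It is a mismatch of 8 percentage points, not of 60 or more. But the section states 448, and the PAM 82% figure fits 448 with a two-sided test: it would be 89% at 560 per arm, or one-sided at 448.
- The overall PAM figure of 98.7% against more than 99% is trivial, and equal arms with the same total give 99.5%. It is minor, but at the stated 2:2:1 the figure is still below 99%.
- The trial would not miss every difference of 1 to 2 points. Between the active arms, SF-36 power is 43% at 1.2 points and 85% at 2.0. This stands: the high miss rates apply to the two named three-arm patterns only.
- The plan does not claim that a null result shows equivalence, and it commits to confidence intervals. This also stands. The over-reading is a risk, not something the plan asserts.

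None of these points supports the two ANOVA figures.

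**Conclusion.** The concern holds. At the plan's own sizes and SDs, with two-sided 0.05 assumed, overall power is 25% where the plan says more than 90% (SF-36) and 21% where it says more than 80% (PAM): overstatements of about 65 and 60 percentage points. The trial would miss those two patterns about 75% and 79% of the time. Spreads detectable at the claimed power are about 2.3 to 2.4 times those stated. No sample-size basis or alpha that was tried closes the gap at the stated SDs.

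The 1.7-point SF-36 claim is overstated by 8 points (72% against 80%) and matches the sample before attrition. The overall PAM figure is a minor discrepancy.

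How the ANOVA errors arose cannot be known from the documents. One possibility for PAM is that the SF-36 SD of 10 was used in place of 20.9: with the enrolled sample that gives 80.6%. The sample size and the conclusions at the hypothesized effects are not disturbed.

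**What to change.** In Sample Size and Power Calculations, replace the affected statements with figures on one declared basis (448/448/224, two-sided 0.05 if that is the intended level):

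- SF-36, active arms: 80% power for a difference of about 1.9 points (effect size 0.19).
- SF-36, three arms: about 90% power for means 6.4, 5.0 and 3.6, noting 25% at 5.6, 5.0 and 4.4.
- PAM, three arms: about 80% power for means 4.5, 8 and 3.4, noting 21% at 6.5, 8 and 6.
- PAM, three arms at the hypothesized increases: 98.7% in place of more than 99%.

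The replacement means keep the shape of the originals; other sets would serve equally well. State the alpha level and sidedness of the main tests and the n behind each power figure.

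The cost is a text correction. The stated sensitivity becomes less favourable; sample size, design and conduct do not change.
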